#### 9.4.6 **Focus group discussions and in-depth interviews**

Discussions during IDIs and FGDs will be recorded and subsequently transcribed. Qualitative data will be managed and analysed using directed content analysis whereby transcripts will be interrogated for specific and emergent themes. The interview guides and conceptual framework will be used to create an initial set of predetermined codes for the domains of potential barriers to high ATSB and LLIN coverage. Data will be coded and organized by theme and respondent type using Microsoft Excel or NVivo. Transcripts will be entered into an Excel file by transferring each codable unit to a separate cell on a line with additional cells containing information on the respondent (interview type, age, sex) for that unit of text. This process of data organization will allow the analyst to become familiar with the transcripts and refine the coding scheme as needed based on the data. Each unit of text will be assigned codes, and sub-codes entered in cells corresponding to the data. Excel Data functions, including Filter and Sort, will be used to organize data according to theme, review data within each assigned code, and make adjustments to coding. When coding is complete, a synthesis of data within each code will be drafted. Patterns among themes and across types of respondents will be identified and interpreted.

#### 9.4.7 Economic evaluation

Both financial and economic costs will be calculated. Costs will be classified as capital or recurrent and traded vs non-traded. Capital costs will be annuitized and discounted using a 3% rate. These costs will be expressed in a common currency and year (2019 US dollars). Additionally, they will be converted into purchasing power parity adjusted International Dollars for internal comparison. Costs will be combined with efficacy measures from the trial to estimate incremental cost-effectiveness measures.

#### 9.4.8 Harms

The main risks associated with the intervention are the risk of physical contact or ingestion of the bait by humans, animals, and/or non-target arthropods, particularly the local bee population. Continued entomological monitoring of non-target insect populations and ongoing monitoring of trial sites for misuse or product loss will be conducted. The statistical analyses of harms to study participants will consist of evaluating the number of AEs and SAEs related to physical contact or ingestion of the bait. analysed

## 10 METHODS: MONITORING

---

### 10.1 TRIAL GOVERNANCE

#### 10.1.1 Trial steering committee

The ATSB project is governed by a steering committee with members from the Bill and Melinda Gates Foundation, IVCC, Westham Co., PATH, the University of Bamako, and two external expert advisors (one epidemiologist and one entomologist). The steering committee meets quarterly to discuss all aspects of the project, including study protocol and procedures, additional external reviews and reviewers (e.g. WHO VCAG), product and production issues, timeline and deliverables, and review of available data.

#### 10.1.2 Data safety and monitoring committees

An independent data safety monitoring board (DSMB) will be established to monitor implementation. The board will consist of at least four independent experts in malaria vector control, entomology, the conduct of community trials, biostatistics, and epidemiology. The members of the DSMB will serve in an individual capacity and provide their expertise and recommendations. No independent member of the DSMB shall have any conflict of interest with the study team, the organizations funding or conducting the research, the results of the research, or the ATSB manufacturer (Westham Co.).

The primary responsibilities of the DSMB will be to periodically review and evaluate the accumulated study data for participant safety, study conduct and progress, and, when appropriate, efficacy. The DSMB will be responsible for making recommendations to investigators and participating in research ethics committees concerning the continuation, modification, or termination of the trial. The DSMB will be guided by a charter. This charter will include statistical monitoring guidelines that will guide recommendations about the trial's termination or continuation. These procedures will include guidelines for termination for futility and termination for safety reasons (see Section 9.4.1, Interim Analysis, page 45).

## 10.2 TRIAL MONITORING AND AUDITING

### 10.2.1 Trial monitoring

External clinical trial monitoring visits are provided by the sponsor at trial initiation, and then regularly (at least yearly) thereafter and at trial closeout, or more frequently if so required; e.g. if the trial fieldwork is about 24 months, this means that the site is visited approximately four times by external monitors. The results from each monitoring visit will help inform whether more frequent or earlier repeat visits are required.

### 10.2.2 Auditing

The independent trial monitoring process will be audited by a study staff from the sponsor's research office at LSTM in Liverpool, UK. The auditor may choose to accompany the clinical monitor during at least one of the site visits to determine if more auditing visits are required.

### 10.2.3 Role of sponsor

The sponsor reserves the right to suspend temporarily or prematurely discontinue this study at any time for reasons including, but not limited to, safety or ethical issues or severe non-compliance. If the sponsor determines such action is needed, it will discuss this with the investigator and the funder (IVCC). When feasible, the sponsor will provide advance notification to the investigator of the impending action prior to it taking effect. The sponsor will promptly inform the ethics committees and provide the reason for the suspension or termination.

## 10.3 SAFETY MONITORING AND REPORTING

### 10.3.1 Adverse events and serious adverse events

Adverse events (AEs) and serious adverse events (SAEs) will be recorded in the study cohort during home visits and sick visits. Since this is not a trial involving a human intervention, these AEs and SAEs will not be reported in an expedited manner to the DSMB, sponsor, ethics committee or regulator. The exceptions are AEs or SAEs related to a physical interaction with ATSBs or ingestion of ATSB materials. Any ingestion of ATSB material will be considered an event that requires expedited reporting regardless of the seriousness of the event. Thus both SAEs or AEs related to physical interaction with ATSBs or ingestion of ATSB materials will be reported by the principal investigator to the DSMB, sponsor and ethics committee/institutional review boards within 72 hours. Study staff will be trained to report such events to the principal investigator in an expedited manner. Participants will also be instructed to contact the study staff if ingestion were to occur. All other AEs and SAEs not related to a physical interaction with ATSBs or ingestion of ATSB materials will be reported at the time of continuing review.

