To determine if ATSB deployment plus universal LLIN coverage compared to universal LLIN coverage alone reduces malaria transmission or affects insecticide resistance	
 
Entomological outcomes including malaria vector densities, the proportion of females older than three gonotrophic cycles, sporozoite rate, EIR and markers of insecticide resistance
 
Antibodies against merozoite surface protein-1 (MSP-1), circumsporozoite proteins (CSP) and other malaria antigens
 
Molecular measurements including, but not limited to, 24-single-nucleotide polymorphisms (24-SNP) barcodes for the complexity of infection
 
Mosquito salivary antigens for biting rates
 

5.2.2 Safety	
Assess the safety of ATSBs on humans	
 
Adverse events associated with misuse or loss of ATSBs.
 

Assess the safety of ATSBs on non-target insects	
 
Continued entomological monitoring of non-target insect populations
 

5.2.3 Ethnographic evaluation	
To understand the acceptability and potential factors that influence ATSB coverage	
 
The proportion of ATSBs that have been moved/removed
 
The proportion of household heads who perceive ATSBs as safe and effective
 

Assess the acceptability of ATSBs by communities and other stakeholders	
 
Identification of potential barriers to uptake and consistent ATSB coverage,
 
Assessment of the impact of ATSBs on the coverage and use of existing malaria control interventions (e.g. LLIN, IRS, treatment-seeking behaviour)
 

5.2.4 Health economics	
Estimate the cost-effectiveness of deploying ATSBs for malaria control.	
 
Incremental cost-effectiveness of ATSB above the standard of care measured through costing of intervention and efficacy outcomes
 

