### 7.8.1 Malaria case incidence cohort

#### 7.8.1.1 *Main trial*

The sample size was calculated using the 'Tests for the Difference Between Two Poisson Rates in a Cluster Randomized Design' module in PASS 2020 (©NCSS, Kaysville, Utah). The observed event rate in this age group was 1,128 per 1000 person-years in the control arm of a recently completed mass test-and-treat trial in this area. A more conservative event rate of 845/1000 will be used, which is 25% lower than the previously observed event rate of 1,128/1000 person-years. This is done to account for an estimated 7.4% overall reduction in event rates in children 1-<15 years due to the implementation of the RTS,S/AS01E vaccine (vaccine efficacy 39.0%) in two-third of the study area in children 1-<5 years of age (28.6% of the sample study cohort) ( $0.39 \times 0.67 \times 0.286 = 0.074$ ), plus a further 17.6% reduction in malaria due to unforeseen changes in environmental factors, or boosting of other malaria control measures such as the scaling up of integrated community-based case management. The coefficient of variation in this previous study was 0.4.

A total sample size of 2,240 person-years (1,120 per arm, or 28 person-years per cluster) is required to detect a  $\geq 30\%$  reduction in the incidence of clinical malaria among children aged 1-<15 years (the primary outcome) from 845 per 1000 person-years in the control arm to 592 in the intervention arm over two years, allowing for 20% loss of person-time due to LTFU, or exclusion of person time after a clinical event treated with artemether-lumefantrine during a six month follow-up period resulting in 1,760 person-years completed (22 person-years per cluster, 880 person-years per arm) (80 clusters [40 per arm], CV=0.4 in both arms, two-sided  $\alpha=0.049$ , power=90%). No sample size inflation is required two allow for two interim analyses because a similar sample size is needed (2,240) for a study with a final two-sided  $\alpha$  of 0.049 as for a study with a single analysis using a two-sided  $\alpha$  of 0.05.

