The intention is to follow each child for 6.5 months. This includes two weeks of lead-in time that do not contribute to the analysis. These are the first two weeks after the initial presumptive treatment with artemether-lumefantrine to clear any existing parasitaemia. This will then be followed by six months of follow-up time that contribute to the analysis. We will use a more conservative average follow-up time of five months per participant to allow staggered enrolment of participants over time. This means that not all children towards the end of the 2-year trial will complete the full 6.5 months. The 2,240 person-years will thus be obtained by sampling approximately 67.2 individuals for an average of five months each in 80 clusters ( $67.2 \times [5/12] \times 80 = 2,240$ ).

The same sample size will also have 80% power to detect a 26% reduction from 845 to 622 per 1000 person-years with all other parameters kept the same, or 80% power to detect a 30% reduction if the CV was 0.488 instead of 0.4. Similarly, the study would have at least 80.0% power to detect a significant difference at the first interim analysis when 50% of the events have occurred in the control arm if the effect size is 41.2% instead of 30% ( $\alpha=0.001$ , using Haybittle-Peto type boundaries, see 9.4.1, Interim analysis, page 44).

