#### 9.1.6 ATSB Intervention monitoring

1. ATSB monitoring assistants will be trained on proper installation, adjustment, and removal and transport of ATSBs on structure walls, administering an ATSB questionnaire, and responding to questions or concerns raised by household members.
2. After administering informed consent and ATSB installation community-based, ATSB monitors will visit households in intervention clusters on a monthly basis
3. ATSB monitors will complete a questionnaire programmed onto a tablet or electronic data capture form to assess the presence of each ATSB and/or whether it has incurred any damage
4. If an ATSB has been damaged, the monitor may photograph the damaged ATSB
5. Damaged or missing ATSBs will be replaced by ATSB monitors at each visit
6. ATSB monitors will instruct the head of the household to contact the study team if an ATSB is damaged or is missing between each visit so that the ATSB monitor can return to replace it to ensure high ATSB coverage rates
7. ATSB monitors will additionally respond to any questions or concerns that household members have about the ATSB or the trial. They will refer questions they are unable to answer to the field supervisor for further consideration and response.

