## Overview of human health risk

The use of dinotefuran in sugar feeders under normal conditions of use is not expected to present an unacceptable risk to users handling the product (placing and removing after use) or to residents living in the community.

Dinotefuran is contained between a polyester/polyethylene laminate and an impermeable film membrane. There is not expected to be any leakage of dinotefuran to the surface of the film (see overview of environmental risk below). Thus, the bait station (product) can be handled safely providing that the integrity of the product is maintained. It will be positioned out of reach of young children and therefore the risk of tampering and possible inadvertent exposure from misuse is considered to be low.

However, as a worst case assessment it is assumed that a child may get hold of one or more products and deliberately break them open to ingest the sugar bait. Each product contains 100 g of sugar/fruit juice solution and 0.1% dinotefuran (0.1 g). The following assessment calculates the maximum amount of sugary fluid that can be ingested before exceeding the acute reference dose (ARfD) or the rat LC50 value for dinotefuran (1.25 mg/kg bw and 2000 mg/kg bw, respectively; US EPA Fact Sheet, 2004 and Durkin, 2009).

$$\begin{aligned}
 &= \frac{\text{ARfD (mg/kg bw)} \times \text{bodyweight (kg)} \times 100}{\text{Concentration of a.s. in product (\%)}} \\
 &= \frac{1.25 \text{ (mg/kg bw)} \times 10 \text{ (kg)}^2 \times 100}{0.1 \text{ (\%)} \times 1000} \\
 &= 12.5 \text{ g of sugary fluid}
 \end{aligned}$$

In this worst case scenario the ARfD would be exceeded 8-fold if the whole content of one bait station was consumed. This represents a risk of a potential adverse effect and therefore, it will be important to mitigate the risk by good product stewardship and education of the community. It is unlikely to lead to a significant poisoning incident given the margin of safety built into the ARfD. The potential for acute poisoning can be calculated by estimating the maximum amount that could be ingested at the rat LC50 of 2000 mg/kg bw. The ARfD is replaced by the LC50 in the above calculation.

$$\begin{aligned}
 &= \frac{2000 \text{ (mg/kg bw)} \times 10 \text{ (kg)}^1 \times 100}{0.1 \text{ (\%)} \times 1000} \\
 &= 20,000 \text{ g of sugary fluid (200 bait stations)}
 \end{aligned}$$

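### Harm from bait exposure is actively sought only in the child cohort, about 3.5–7% of household-time under ATSB; elsewhere it depends on someone volunteering a report

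*Protocol*

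**What the plan says.** **Endpoint.** Section 5.2.2 (Table 1) sets the human-safety endpoint as "Adverse events associated with misuse or loss of ATSBs". Section 6.3.11 promises systematic documentation of inadvertent exposures among study participants and refers to section 10.3 for how.

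**Where events are recorded.** Section 10.3.1: "Adverse events (AEs) and serious adverse events (SAEs) will be recorded in the study cohort during home visits and sick visits". Sections 7.3.2.1 and 9.1.2 limit the cohort to one resident aged 1 to under 15 years per selected household, in core areas. Monthly cohort visits ask about recent illness, including AEs and SAEs (9.1.2.3). A specific question on touching or ingesting bait is stated for sick visits (9.1.2.4).

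**Who is exposed.** Stations go to all consenting households in the core and buffer areas of the 40 intervention clusters (7.3.3.1, 7.6.1.1).

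**What monitors do.** Section 9.1.6: "ATSB monitors will visit households in intervention clusters on a monthly basis". Their questionnaire is described as recording whether each station is present and whether it is damaged. Section 7.6.1.3 adds that they record questions or concerns raised by the household.

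**Other channels.** Section 10.3.1 tells participants to contact staff if ingestion occurs, trains staff to report such events, and requires a report within 72 hours. Section 9.4.8 adds monitoring of sites for misuse and product loss, and plans a count of AEs and SAEs related to contact or ingestion.

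**The concern.** The endpoint concerns people in homes where stations hang, but the only people the protocol describes being asked are cohort children. Infants under 1 year, adults, siblings of cohort children, other core households and the whole buffer have no described active ascertainment. Section 6.3.11 promises systematic monitoring, yet the section it cites places the recording in the cohort.

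This is a data-collection matter. A statistical analysis plan can define how events are counted, but it cannot recover exposures nobody asked about. A low count would then be ambiguous: few exposures, or few reports. The results go to WHO's advisory process (section 4), where product safety in ordinary homes is a natural question.

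**Working it through.** **Step 1. Reproduce the plan's person-time.** Section 7.8.1.1 states "A total sample size of 2,240 person-years (1,120 per arm, or 28 person-years per cluster) is required", obtained by "sampling approximately 67.2 individuals for an average of five months each in 80 clusters".

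- 67.2 × (5/12) × 80 = 2,240 person-years; half is 1,120 per arm. This agrees.
- After planned loss: 22 per cluster × 40 = 880 per arm. As a check, 880 × 0.845 = 743.6, the plan's 744 expected control-arm events.

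**Step 2. Household-time under ATSB in the intervention arm.** Inputs: 40 clusters, 200–400 households per cluster (section 6.1), two years (section 2.4.1).

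- Low: 40 × 200 × 2 = 16,000 household-years
- High: 40 × 400 × 2 = 32,000 household-years

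**Step 3. Share with a child under active recording.** With one child per household, cohort child-time equals household-time.

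| Cohort person-years, ATSB arm | 200 households per cluster | 400 households per cluster |
|---|---|---|
| 1,120 (planned) | 1,120/16,000 = 7.0% | 1,120/32,000 = 3.5% |
| 880 (after planned loss) | 880/16,000 = 5.5% | 880/32,000 = 2.75% |

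The registration table gives 1,200 person-years per arm instead of 1,120; that would make the range 3.75–7.5%.

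**Step 4. Two other ways to express the reach.**

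- As a share of all residents' time it is smaller. The protocol gives no household size; assuming 3 to 5 people, it runs from 1,120/(32,000 × 5) = 0.7% to 1,120/(16,000 × 3) = 2.3%.
- As a share of households that ever contribute a cohort child it is larger: 67.2 × 40 = 2,688 children over 8,000–16,000 households is 34% to 17%, if no household is sampled twice. Each contributes for about five months, and only one member is followed.

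**Step 5. What catches an exposure outside the cohort.** Two routes are described: the household contacts staff, or a concern is raised with a monitor. The instructions listed for ATSB households (6.3.7.1, 7.6.1.1, 9.1.6, 11.3.3.1) deal with damaged, missing or taken-down stations; none of these lists includes reporting contact or ingestion. Monitoring of misuse and loss tracks stations, not exposed people.

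**Step 6. How often monitors call.** Sections 7.6.1.3, 9.1.6 and 11.3.3.1 have monthly visits to intervention households. Section 6.3.7.2 has either all stations or a sample checked about monthly. Table 7 has a visit every two months.

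**Step 7. Annex IV.** For a 10 kg child, the acute reference dose corresponds to 12.5 g of fluid, and a station holds 100 g: 100/12.5 = 8. Hence "the ARfD would be exceeded 8-fold if the whole content of one bait station was consumed". The same paragraph calls this a potential adverse effect to be mitigated, and judges a significant poisoning unlikely given the safety margin in the reference dose.

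**The case against.** The strongest reply is that the plan is proportionate. The intervention is not directed at people, expected risk is minimal (9.4.1.4), and the Annex IV worst case is a child of 1 to 3 years, an age the cohort follows. Any ingestion is reportable within 72 hours whatever its seriousness, and the trial population in section 7.3 is all residents, so the reporting instruction need not stop at the cohort. That stands as far as it goes: safety information can reach the trial from outside the cohort. It arrives unsolicited, however, and no section describes asking for it.

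Four stronger readings are tempting, and the documents do not support them.

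- A reader might infer that adverse events are collected only in the cohort. Spontaneous ingestion reports and recorded household concerns reach further. The 3.5–7% is the share under active recording, not the full reach of the safety data.
- A reader might infer that the monitoring form contains no exposure question. The form is not shown; only its description in 9.1.6 lacks one.
- A reader might compare zero-event upper bounds per child-year in the cohort with bounds per household-year if every household were asked, and call the difference gained precision. A directly followed child and a proxy report for a whole household are different units, and the second bound also assumes that every household is visited.
- A reader might take the eightfold figure as evidence of serious hazard. Annex IV's own conclusion is that significant poisoning is unlikely.

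**Conclusion.** The point holds as a gap in active ascertainment. As written, the protocol seeks adverse events in cohort children, about 3.5–7% of household-time under ATSB (2.75–5.5% after planned loss), and relies on volunteered reports for everyone else living with the stations. Its human-safety endpoint is therefore not systematically ascertained in most of the exposed population, and analysis cannot repair this afterwards.

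The percentages assume that all 200–400 households per cluster consent and host stations for the full two years; refusals would raise the share. The conclusion about the monitors rests on the protocol's description of their questionnaire. The point concerns completeness of safety data. It does not show that the product is unsafe or that exposures will be missed in any known number.

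**What to change.** 1. In 9.1.6, add a structured item to the ATSB monitoring form: any skin contact with, or ingestion of, bait by any household member since the last visit, and any illness after it. If the form already has such an item, say so in 9.1.6.
2. Route positive answers into the existing 72-hour report in 10.3.1.
3. State in 10.3.1 and 9.4.8 that exposure events from all monitored intervention households enter the safety endpoint, reported separately from cohort AEs, because the two are collected differently.
4. Reconcile the three statements of monitoring frequency and coverage (7.6.1.3, 9.1.6 and 11.3.3.1; 6.3.7.2; Table 7). The item works at any of these intervals, but the recall period and the share of households asked depend on which applies.
5. Wherever the eightfold figure is cited, give Annex IV's conclusion on poisoning with it.

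Cost: one or two questions on an existing electronic form, a short training note, a little interviewer time at visits already planned, and a protocol amendment. No new staff or visits are needed for the households the plan already has monitored. The drawback is that events would be proxy-reported by whoever is at home, so they are less certain than those recorded in the cohort.

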##### 9.1.2.1 *At recruitment/enrolment*

- Informed consent will be administered to the parent/caregiver, and assent to the participant if he/she is 13-<15 years of age
- A fingerprick blood sample (~250µL or 1mL) will be collected to perform an RDT and to prepare approximately five dried blood spots (DBS) on filter paper for subsequent molecular and potentially serological testing and for evaluation of mosquito salivary antigens
- All cohort members will be treated with artemether-lumefantrine (AL; first-line antimalarial in Kenya) irrespective of their RDT result to clear any subpatent infections that may exist
- A questionnaire will be administered to the head of the household to assess household assets for the construction of socio-economic status (SES) categories and to assess household malaria control measures (e.g. number of LLINs, housing construction)
- A questionnaire will be administered to the parent/caregiver and/or the participant to assess activities of interest, including medical and vaccination history, medication use, inclusion in other clinical trials, care-seeking behaviour, LLIN use, daily commuting and travel information, and information about the structure that the participant sleeps in
  - A photograph will be taken of vaccination history and pertinent medical records from the maternal child health booklet or other records

- For participants enrolled in the HDSS or clinical studies, we will link the cohort data to their study/HDSS records
- For young women of childbearing age (12-14 years), pregnancy status will be evaluated in a private and confidential location through the following algorithm:
  - If the woman has had menarche, her last menstrual period was  $\geq 6$  weeks ago, and if she has any suspicion that she may be pregnant, then she will be offered a urine pregnancy test
  - If she declines or is found to be pregnant, she will be considered ineligible for the cohort
- A photograph may be taken of the participant to create a study identification badge that the participant will keep for identification by study staff for scheduled and sick visits

9.1.2.2 *Parasite clearance confirmation visit (2 weeks after enrolment)*

- Before this visit, the study team will call the cohort member to remind them of the upcoming visit and reschedule if necessary. Up to three visit attempts will be made to complete the parasite clearance confirmation visit.

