- For women of childbearing age, pregnancy status will be evaluated as described in the enrolment visit section. Those in whom a pregnancy test is indicated but who decline and those who have a positive pregnancy test will be withdrawn from the cohort. These women

may opt to be visited and evaluated for malaria, free of charge for the duration that they would have been in the cohort.

- A questionnaire will be administered on a tablet or smartphone to the participant or his/her parent/guardian, including questions about the history of recent illness (including AEs and SAEs), care-seeking, LLIN use, and travel and commuting history. If the cohort member sought care between scheduled visits, we will copy any relevant information from these health records to evaluate any malaria diagnostics performed and antimalarial treatment given
- A follow-up visit in four weeks time may be scheduled at this time. Parents/guardians and the participant will be reminded to call the study staff at the number provided on the consent form if the participant becomes ill before the next scheduled visit.
- The limited care provided by the study team includes any care related to study procedures, malaria illness, or other uncomplicated acute illnesses such as acute respiratory or gastrointestinal disease. The study will not be responsible for the care of pre-existing conditions or chronic or traumatic conditions diagnosed during the trial.

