#### 9.4.1.4 *Stopping for harm*

The trials do not include formal stopping rules based on harm. The intervention is not targeted to humans, and the expected risk to trial participants is expected to be minimal. However, this does not preclude the DSMB from stopping the trial for harm should unforeseen consequences of the ATSB or trial procedures lead to harms.

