#### 11.3.1.3 Risks associated with the protection of privacy and confidentiality

Collection of household and individual identifying information is necessary for the follow-up procedures. Geolocations of all households involved in the intervention and surveys will be collected. The collection of this information poses a potential threat to the confidentiality of individual data. Interview forms will contain little information that would generally be considered to be sensitive. Notably, there is no stigma associated with malaria infection status in the study communities. However, there is a risk that the privacy of an individual could be compromised during the administration of a questionnaire.

Table 7: Risks associated with each type of data collection

Type of data collection	Description	Risk
Census enumeration	Household questionnaire	No risk
ATSB monitoring	Monitoring visit once every two months to confirm installation and assess the condition of the ATSB	No risk
Cohort study enrollment and monitoring	Brief questionnaire Fingerstick for RDT and dried blood spot collection	Minimal risk from the finger stick Side effects of malaria treatment Inadvertent pregnancy disclosure
Household survey	Household questionnaire Fingerstick for RDT and dried blood spot collection	Minimal risk from the finger stick

		Side effects of malaria treatment Inadvertent pregnancy disclosure
Focus group discussion	Semi-structured group discussion with recording and transcription of the conversation	No risk
In-depth interview	Semi-structured interview with recording and transcription of the conversation	No risk
Entomological monitoring	Mosquito traps will be placed inside and outside of homes and will trap mosquitoes during peak biting hours beginning in the early evening through the early morning.	No risk
Entomological Monitoring	Indoor and outdoor human landing catches through the night	Minimal risk of mosquito bites and malaria infection
Economic evaluation	Collection of intervention cost data	No risk

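### Expedited safety reporting leaves out serious events from study-given antimalarials, on a no-human-intervention premise that the protocol's own procedures contradict

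*Protocol*

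**What the plan says.** Section 10.3.1 records AEs and SAEs in the cohort at home and sick visits. It then states: "Since this is not a trial involving a human intervention, these AEs and SAEs will not be reported in an expedited manner". One carve-out follows: "The exceptions are AEs or SAEs related to a physical interaction with ATSBs or ingestion of ATSB materials". Those events go "to the DSMB, sponsor and ethics committee/institutional review boards within 72 hours". Everything else is left to continuing review, with no interval given.

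Other sections bear on this:

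- **9.1.2.1 (also 6.3.3.1):** all cohort members are given artemether-lumefantrine "irrespective of their RDT result to clear any subpatent infections that may exist".
- **9.1.2.2:** children found positive at the two-week visit are given second-line treatment by study staff.
- **9.1.5.2:** landing-catch collectors are given weekly mefloquine.
- **Table 7 (section 11.3.1.3):** the cohort row lists "Side effects of malaria treatment" among the risks.
- **9.4.1.4:** there is no formal stopping rule for harm, but "this does not preclude the DSMB from stopping the trial for harm should unforeseen consequences of the ATSB or trial procedures lead to harms".
- **9.4.8:** the harms analysis for participants consists of "evaluating the number of AEs and SAEs related to physical contact or ingestion of the bait".
- **10.1.2:** the DSMB periodically reviews accumulated data for participant safety, without restriction to bait events.

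**The concern.** The reason given for withholding fast reporting does not describe this study. The randomised product targets mosquitoes, but taking part in the cohort means taking a drug supplied by the study, in many cases without a positive test. The protocol treats that drug as a risk elsewhere. Table 7 lists its side effects, and section 11.2.4 excludes pregnant girls because of the presumptive course.

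Read literally, the rule sends any bait ingestion to three bodies within 72 hours, however trivial, while a serious drug reaction in a child is not expedited to anyone. At stake is how quickly the bodies responsible for participants learn of harm from a procedure that the study itself imposes.

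**Working it through.** **Exposure.** The inputs are from 2.4.1, 7.8.1.1 and 7.8.1.2.

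- Main cohort: 67.2 children per cluster × 80 clusters = 5,376, which reproduces the plan's figure. As a check, 67.2 × (5/12) × 80 = 2,240 person-years, also as stated.
- Baseline cohort: 11 × 100 clusters = 1,100.
- Planned presumptive courses: 5,376 + 1,100 = 6,476.
- Section 7.4 allows about 20% for refusal, loss and withdrawal combined. If all of that were refusal before treatment, the count would be 0.8 × 6,476 ≈ 5,181.

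**Treated without a positive test.** No RDT prevalence is given for ages 1 to under 15. The nearest figures are 36.5% in under-fives (7.1) and all-age values of 29% and 47.3% (7.8.2). Assuming that 29% to 47.3% test positive at enrolment, between 5,376 × (1 − 0.473) ≈ 2,833 and 5,376 × (1 − 0.29) ≈ 3,817 main-trial children are treated without a positive test.

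**How often the gap could bite.** The documents give no rate of drug-related SAEs. As an assumption only, take r = 1 per 10,000 to 1 per 1,000 courses, independent between courses, with n = 6,476.

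| r | Expected SAEs, n × r | P(at least one), 1 − (1 − r)^n |
|---|---|---|
| 1/10,000 | 0.65 | 48% |
| 1/1,000 | 6.5 | 99.8% |

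None of these would fall under the 72-hour rule.

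**Tracing one drug-related SAE through the text.**

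1. *Recording.* Section 10.3.1 covers home visits, and the two-week contact is a home visit, so recording is possible. But the two-week procedure list (9.1.2.2) has no AE question, whereas the monthly list (9.1.2.3), starting at week four, has a questionnaire "including questions about the history of recent illness (including AEs and SAEs". The recording sentence speaks of the cohort, so it does not name the landing-catch collectors.
2. *Expedited report.* The event is not bait-related, so it is excluded.
3. *Later report.* It goes to continuing review, interval not stated, and possibly to a periodic DSMB review, timing not stated (10.1.2).
4. *Analysis.* Section 9.4.8 leaves it out.
5. *Action.* Section 9.4.1.4 contemplates stopping for harm from trial procedures, but no prompt report feeds that decision.

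**The case against.** The best defence is that the randomised intervention is the bait, which acts on the vector (9.4.1.4, 11.3.5). Artemether-lumefantrine is Kenya's first-line drug, given in both arms as part of outcome measurement, so centring the harms comparison on the bait is a reasonable choice. The DSMB charter is not shown, and section 11.1 binds the study to GCP principles and Kenyan requirements, so practice may be better than the text. This explains the wording but does not repair it. The reporting rule is stated, and its exception is closed.

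The objection does stand against several stronger readings that a reader might infer:

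- *The DSMB never sees drug-related events and cannot act on them.* Not supported. Section 10.1.2 gives it periodic review of all accumulated safety data. What is missing is prompt reporting and a defined timing.
- *Nothing can be captured before week four.* Not supported. Home visits and participant-initiated sick visits (9.1.2.4) fall under 10.3.1. The gap is the missing explicit question at week two.
- *Children withdrawn at two weeks are never seen again.* Not so for smear-positive children, to whom a staff member returns with treatment, although no AE check is specified for that contact.
- *The presumptive course is the only drug exposure.* Second-line treatment and mefloquine are others.
- *Treated clinical episodes in follow-up add to the imposed exposure.* At design rates there would be about 880 × 0.845 + 880 × 0.592 ≈ 744 + 521 = 1,265 in the main trial. These are confirmed malaria treated under national guidelines, so they are not counted here.
- *Reporting is delayed by a year.* That would assume annual continuing review, which the protocol does not state.

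**Conclusion.** The point holds in this form: section 10.3.1 gives no expedited route for SAEs related to study-given antimalarials, and the reason it offers conflicts with 6.3.3.1, 9.1.2.1, 9.1.2.2, 9.1.5.2 and Table 7. This is a stated rule that works badly, not detail left to another document. It concerns 6,476 planned presumptive courses, fewer if part of the 20% allowance is refusal, plus the second-line and mefloquine recipients, whose numbers are not given. The number of affected children cannot be derived from the documents, and the SAE counts above rest on assumed rates. The matter is participant protection. It does not touch the primary analysis, sample size, power or alpha.

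**What to change.** Reconcile section 10.3.1 with 6.3.3.1, 9.1.2.1, 9.1.2.2, 9.1.5.2, 9.4.1.4, 9.4.8, 10.1.2 and Table 7:

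- In 10.3.1, delete the premise that no human intervention is involved.
- Extend the existing 72-hour route to SAEs judged possibly related to an antimalarial supplied by the study or to a study procedure. Word the recording sentence so that it also covers the landing-catch collectors.
- In 9.1.2.2, add the existing AE/SAE questions to the two-week visit, to be asked before any child is withdrawn.
- In 9.4.8 and in the DSMB reports, list these events beside the bait-related ones.
- Leave unrelated AEs and SAEs at continuing review.

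No dose, treatment rule or eligibility criterion changes. The cost is protocol wording, one existing block of questions at a visit that already takes place, and a few more relatedness assessments and expedited reports.
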